### **7.8 Duration of Study Participation**

Study participation will end at the Day 360 post-HCT visit (1 year post-HCT) unless the subject voluntarily withdraws or their parent(s)/legal guardian(s) voluntarily withdraws them from the study or disease relapse occurs and patient discontinues the planned post-HCT follow-up.

If a subject or their parent(s)/legal guardian(s) withdraws consent to participate in the study or care is no longer provided by the enrolling institution, attempts will be made to obtain survival data through 1 year post-HCT.

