2	12/03/2014	
 
• Throughout protocol: Revise Day 100 to Day 90 and if appropriate generalize the time point as 3 months
 
• Throughout protocol: Delete references to study entry as “day of admission for transplant”
 
• Throughout the protocol refer to affiliate institution as Fred Hutchinson Cancer Research Center as this is where the PI and IRB are located, although the study will continue to be conducted at Seattle Children’s Hospital
 
• Section 6.2, Randomization Day 90 Post-HCT Visit: Add statements that we will request to collect data from routine tests (DXA scans done at 1 year post-transplant and other relevant data) from subjects who are not eligible for or refuse randomization at Day 90
 
• Section 7.2, Calcium: Clarify how calcium level will be calculated if
 
	yes

revision #	version date	summary of revisions	consent form changed
		
subject's total calcium level is below the normal range.
 
 
• Section 7.6 and 7.7, Duration of Study Treatment and Participation Update and clarify
 
• Section 8, Study Related Tests and Procedures: Update
 
• Section 8.1.3 Subject Compensation: Update
 
• Section 8.2.5 Diet and Activity Questionnaire: Update to reflect that subjects will receive paper copies of forms
 
• Section 8.3.2 Specimen Processing and Storage: Clarify that research samples will be stored for batch testing and destroyed once testing is complete.
 
• Delete appendix V – Targeted Toxicities as replaced by a more detailed CRF
 
	

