### **6.2 Randomization (Day 90 Post-HCT Visit +/- 14 days)**

Randomization to pamidronate (Pamidronate Group) or no pamidronate (Control Group) will occur at Day 90 (+/- 14 days) by the institutional study coordinator based on the randomization schedule developed by the study statistician and entered into OnCore.

A brief review of continuing eligibility will be done and subjects will not be eligible for randomization if one or more of the following are true:

- Vitamin D ( $D_2+D_3$ )  $<20$  ng/ml as use of pamidronate is contraindicated due to potentially higher risk of hypocalcemia. Levels should be measured within 14 days prior to randomization.\*\*†
- serum creatinine is  $> 2$  times the baseline value (at Study Entry) - perform within 14 days prior to randomization
- an investigational study drug or agent, including biphosphonates, Denosumab, or Teriparatide, was administered within the previous 4 weeks or is planned for use during study participation (Day 90 through Day 360)
- positive pregnancy test (performed within 14 days prior to randomization)
- Inability to successfully complete a DEXA scan
- the parent or adult patient refuse randomization
- disease relapse has occurred

The randomization will be stratified by age with 2 strata:  $< 10$  years old and  $\geq 10$  years old.

If the patient is ineligible for or refuses randomization, no further research related procedures or treatment will occur after the Day 90 visit; however permission to continue review of the patient's medical record through the Day 360 visit for routine clinical information is embedded within the consent form document. This information will be collected only if the patient continues care at the enrolling

institution. Patient care will be at the discretion of the treating physician(s) and independent of this study.

OnCore will automatically generate an email alerting key study personnel of the randomization (or lack of).

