## **12 Statistical Considerations**

### **12.1 Sample Size**

Sixty (60) subjects total (30 each in the Control and Pamidronate groups) gives 80% power to detect a difference between groups of 0.75 standard deviations (SDs)

describing variation in LBMC within study group after adjusting for height, age, sex, Tanner score, and race. Adjusting for age and sex, this SD is 5-8g (46, 47); adjusting further for race and height should reduce this SD by about half (48-50). This gives a within-group SD of about 2.5-4g and a detectable difference of 2-3g. To have 60 evaluable subjects, 192 need to be screened to allow for a 50% consent rate, 10% death rate by Day 90, 20% death rate between Day 90 and Day 360, and 10% drop out after randomization.

Anticipated Enrollment Over Duration of Study

	Screen	Study Entry Day -14 a	Day 7	Day 14	Day 21	Day 90	Day 180	Day 270	Day 360
Total	192	96	96	96	96	86	86	86	60
University of Minnesota (UMN)	96	48	48	48	48	43	43	43	30
Fred Hutchinson Cancer Research Center	96	48	48	48	48	43	43	43	30
a Day 0 is the day of hematopoietic cell transplantation (HCT).									

According to data from 2011 to 2012, 36 allogeneic transplants have been performed at UMN and 37 have been performed at Fred Hutchinson Cancer Research Center. It is expected that screening 28 patients per year will be feasible for both sites.

It anticipated that enrollment will take 3.5 years.

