## 12.2 Subject Population(s) for Analysis

All randomized subjects will be included in the primary analysis according to their randomized treatment assignment, consistent with the principle of intention-to-treat.

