## 12.4 Statistical Methods

The primary analysis will compare the Pamidronate and Control groups according to LBMC measured by DXA using all available Day 360 measurements and adjusting for height, age, sex, Tanner score, and race. The analysis will be a multiple linear regression; the primary predictor will be randomized treatment assignment and adjusters listed above. If preliminary analysis shows that LBMC measurements have a grossly non-Gaussian (non- normal) distribution, a transformation of LBMC will be analyzed, most likely  $\log_{10}$  LBMC Secondary analyses will include the following:

- The hypothesis that subjects randomized to pamidronate will have higher total BMD, cortical BMD, trabecular BMD, and estimated bone strength measured by pQCT at 1 year compared to subjects randomized to control (Aim 1 Hypothesis 2) will be tested by applying the foregoing analyses to outcomes measured by pQCT, namely bone strength, total BMD, cortical BMD, and trabecular BMD, but excluding height from the adjusters.
- The hypothesis that cytokine levels will increase rapidly in the first 3 weeks after HCT, preceding an increase in markers of bone resorption (Aim 2 Hypothesis 1) will be tested, for each cytokine, by using all available data for each child (up to 4 measurements from Day -14 to Day 21) and fitting a mixed linear model with a random intercept and time trend for each child and testing whether the average time trend differs from zero.
- The hypothesis that in the Control Group, increased cytokine levels and receptor activator of nuclear factor- $\kappa$ B ligand/osteoprotegerin ratio at 3 weeks will be associated with decreased BMC and BMD at 1 year after HCT (Aim 2 Hypothesis 2) will be tested using linear regressions with dependent variables being each of the BMC and BMD measures at Day 360 and predictors being changes in each of the cytokine levels and RANKL/OPG ratio (from Day -14 to Day 21).
- For the hypothesis that markers of bone resorption will increase in the first 3 months after HCT, will remain elevated until at least Day 180 in the

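### Section 12.2 puts all randomised children in the primary analysis, but 12.1 and 12.4 give about 60 of 86, and no route to a one-year scan is stated for a child who withdraws consent yet stays in care

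*Combined protocol and SAP*

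**What the plan says.** **Analysis set.** Section 12.2 states "All randomized subjects will be included in the primary analysis according to their randomized treatment assignment", citing intention-to-treat. Section 12.4 makes the primary analysis a multiple linear regression "using all available Day 360 measurements and adjusting for height, age, sex, Tanner score, and race".

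**Expected losses.** Section 12.1 allows for "20% death rate between Day 90 and Day 360, and 10% drop out after randomization". Its enrolment table shows 86 children at Day 90, when randomisation takes place, and 60 at Day 360.

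**Randomised children who leave.** Section 7.8 covers two situations, withdrawal of consent and care that is no longer given by the enrolling institution. For both it says "attempts will be made to obtain survival data through 1 year post-HCT" and names no other data. Section 7.7 adds that a child who withdraws after an adverse event is followed until it has resolved or stabilised. Under 7.4.6 and 7.7, children who only stop pamidronate or other study therapy normally remain on study and continue the scheduled procedures.

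**Children never randomised.** For a child who is ineligible for randomisation or refuses it, 6.2 says that the consent form carries "permission to continue review of the patient's medical record through the Day 360 visit for routine clinical information", limited to children still in care at the enrolling institution. The Revision History entry for revision 2 gives "DXA scans done at 1 year post-transplant" as an example of such routine tests. The current 6.2 does not name the scan.

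**Missing outcomes.** The synopsis plans, as a secondary analysis, multiple imputation of missing Day 360 bone mineral content (BMC) and density. Section 12.4 lists multiple imputation for Aims 2 and 3 and for Aim 1 hypothesis 2, and does not list the primary LBMC comparison.

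**The concern.** The population statement and the analysis do not match. A result reported as intention-to-treat on all randomised children would in fact compare, by assigned arm, the surviving children who had a Day 360 scan.

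Deaths leave no outcome to collect. Living children without an outcome are different, because some of that loss may be avoidable. The trial is open-label and the arms carry different burdens: pamidronate children have infusions, post-infusion laboratory tests and safety calls, while controls unwilling to attend non-routine visits can be telephoned instead (8.2.1). Withdrawal could therefore differ by arm and bring selection into the comparison.

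Against that background, the plan states a route to routine records for children who cannot enter the primary comparison, and none for a randomised child who withdraws consent but is still seen at the same hospital.

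**Working it through.** **1. Reproduce the planned flow (inputs from 12.1).**
- Consent: 192 × 0.50 = 96.
- Alive at Day 90: 96 × 0.90 = 86.4 (86 in the table).
- Day 360, with the two later losses added: 86.4 × (1 − 0.20 − 0.10) = 60.5 (60 in the table).

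The plan's figures reproduce. The primary analysis would cover 60/86 = 70% of randomised children.

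**2. Split the 26 losses.**
- Deaths: 0.20 × 86 = 17.2, about 17.
- Drop-outs: 0.10 × 86 = 8.6, about 9. If the 10% applies only to survivors, 0.10 × 68.8 = 6.9, about 7, and about 62 children rather than 60 would have an outcome.
- Missing share among survivors: 8.6/68.8 = 12.5%, or 10% on the second reading.

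About one third of the 26 are living children. The most that any retention rule could reach is about 60 + 9 = 69 (or 62 + 7 = 69), not 86.

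**3. Who falls in the gap.**

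| Child | Provision | Stated route to a one-year LBMC? |
|---|---|---|
| Randomised, stops pamidronate only | 7.4.6, 7.7: normally stays on study | Yes |
| Randomised, care moves away | 7.8: survival | No |
| Never randomised, care moves away | 6.2: no record review | No |
| Randomised, withdraws consent, stays in care | 7.8: survival; 7.7: adverse-event follow-up | No |
| Never randomised, stays in care | 6.2: record review through Day 360 | Possibly, if a routine scan was done |

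The difference in treatment lies in the last two rows only. Section 12.1 does not divide its 10% drop-out by reason, so the number in the fourth row is unknown, between 0 and about 9.

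**4. Power.** Two-sample t-test, equal arms, difference 0.75 SD (12.1), two-sided 0.05 (assumed; 12.1 states neither alpha nor sidedness). The noncentrality is 0.75 × √(N/4) on N − 2 degrees of freedom. For N = 60 it is 0.75 × √15 = 2.90 on 58.

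| N with LBMC | Meaning | Power |
|---|---|---|
| 60 | as planned | 81.5% |
| 65 | about half of 9 recovered | 84.5% |
| 69 | all 9 recovered | 86.7% |
| 86 | all randomised | 93.0% |

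The first row agrees with the 80% in 12.1. Allowing 5 to 10 degrees of freedom for covariates changes it only to 81.4% to 81.2%. On the second reading in step 2, the starting point is 62 children and 82.8%.

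**5. Illustration of bias.** Bias in one arm's mean among survivors = missing share × difference between missing and observed children. Suppose that drop-outs split evenly between the arms and that in one arm only the missing children differ by 1 SD. The bias is 9/69 × 1 = 0.13 SD, falling to 4/69 × 1 = 0.06 SD if about half are recovered. The 1 SD is an assumption with no source in the documents. If the missing children differ equally in both arms, the bias in the treatment difference cancels.

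**The case against.** The strongest reply is that the plan already retains children well, and that the contrast with 6.2 is not like for like. Children who stop drug stay on study, missed Day 180 and 270 questionnaires can be completed by telephone, and adverse events are followed after withdrawal. A child who refuses randomisation has not withdrawn study consent, so a narrower rule after withdrawal may reflect the limits of consent rather than an oversight. The trial is also sized for 60 after these losses. All of that stands, and it confines the point to the group identified above.

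Three stronger readings are tempting, and the documents do not support them.
- **The retention rule costs the trial 26 children.** About 17 are planned deaths, which no rule can recover. The 93.0% power at 86 is therefore not attainable.
- **The plan keeps a known one-year scan for the wrong children and discards it for the right ones.** The scan is named only in the revision log, which describes superseded text. Section 7.8 does not forbid record review. The consent form is not in the file and may already permit it.
- **Nothing is planned for missing primary outcomes.** The synopsis does plan to impute Day 360 BMC as a secondary analysis. The defect is that 12.4 does not carry this through to the primary hypothesis.

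These limits do not rescue 12.2. Its wording is wrong against 12.1 and 12.4 even if no scan is ever recovered, and a secondary imputation would not change who is in the primary analysis.

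**Conclusion.** The point holds in two parts. First, the statement in 12.2 is inaccurate: the primary analysis will contain about 60 of 86 randomised children, and the plan does not say how deaths and living non-completers are to be presented. Second, there is a narrow gap in data collection for randomised children who withdraw consent but remain in care at the enrolling institution.

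The first part rests on the text and on the plan's own arithmetic. The second is inferred from what 6.2 and 7.8 leave unsaid, and the consent form could resolve it. Its benefit is modest and uncertain: 0 to 9 outcomes recovered, hence between no gain and about 5 percentage points of power (86.7 − 81.5 = 5.2). The stated 80% is met without it. The 0.13 SD shows how such bias would scale and is not an estimate of bias in this trial. The change is worth making because it is cheap and acts on the part of the missing data that may be avoidable.

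**What to change.** 1. **Section 7.8 (cross-referenced in 7.7).** Extend the 6.2 records permission to randomised children who withdraw from study visits, remain in care at the enrolling institution and have not refused use of their records. Collect any routine one-year DXA, with height and Tanner stage where recorded, and analyse that LBMC under the assigned arm. Add a sensitivity analysis for scans outside Day 360 ± 30 days or with incomplete covariates. If the consent form already allows this, 7.8 should say so.
2. **Section 12.2.** Define the primary analysis set as all randomised children with a Day 360 LBMC, analysed by assigned arm, expected to be about 60 of 86. Report deaths and living non-completers by arm, and do not describe the set as all randomised subjects.
3. **Section 12.4 and synopsis.** Reconcile the two on whether missing Day 360 LBMC is imputed in a secondary analysis of the primary endpoint.

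The cost is a paragraph in 7.8, a consent-form line modelled on the existing 6.2 permission if one is needed, and short edits to 12.2 and to 12.4 or the synopsis. No visit or scan is added. The downside is that some routine scans may be off-window or lack covariates, which the sensitivity analysis would show.

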## 8 Study Related Tests and Procedures

### 8.1 Schedule of Tests and Procedures

	Screen a	Study Entry b	Day 0	Day 7 (±2)	Day 14 (+ 2)	Day 21 (±2)	Day 90 (±14)	Day 180 (±14)	Day 270 (±30)	Day 360 (±30)
Informed Consent / Assent	X or X									
Physical Examination	X c or X c									X c
Weight	X	X					X	X	X	X
Height		X								X
Medical History	X or X						X	X	X	X
Medication Usage	X or X					X	X	X	X	X
Creatinine	X or X						X	X	X	
Urine or serum Pregnancy Test d,e	X or X						X	X f	X f	X
Diet & Activity Questionnaire		X					X	X	X	X
Adverse Event Assessment							X	X	X	X
Ionized/ or corrected Calcium	X or X						X f	X f	X f	
Vitamin D (D 2 +D 3 )	X or X						X g	X	X	X
iPTH		X					X			X
CTX, P1NP, & OCN		X		X	X	X	X	X		X
Urinary DPD and Creatinine		X		X	X	X	X	X		X
RANKL & OPG		X		X	X	X	X			
IL-6, IL-7, & TNF- $\alpha$		X		X	X	X	X			
DXA h		X					X			X
pQCT i							X			X
HCT			X							
Vitamin D & Calcium Administration j			X-----							X
Randomization – refer to section 6.2							X			
Pamidronate Administration k							X	X	X	
End of infusion (same day) serum calcium							X l	X l	X l	
Post infusion (next a.m.) m serum creatinine and spot urine for albumin and creatinine							X l	X l	X l	
Adverse event assessment by telephone 1 week post infusion (+/-3 days)							X l	X l	X l	

CTX = carboxy-terminal collagen crosslinks; DXA = dual-energy x-ray absorptiometry; DPD = deoxypyridinoline; HCT = hematopoietic cell transplantation; IL = interleukin; iPTH = intact parathyroid hormone; OCN = osteocalcin; OPG =

osteoprotegerin; P1NP = procollagen type 1 amino-terminal propeptide; pQCT = peripheral quantitative computed tomography; RANKL = receptor activator of nuclear factor- $\kappa$  B ligand; TNF- $\alpha$  = tumor necrosis factor alpha.

a Screening will occur during the pre-HCT work-up.

b Evaluations and tests only in the Study entry column are performed only after consent is signed and must be completed within 4 weeks (6 weeks for DEXA) prior to beginning pre-HCT conditioning regimen. If DEXA cannot be completed prior to conditioning, this will not be considered a protocol deviation

c Including Tanner staging of pubertal development.

d Females >10 years only.

e If documentation of a negative pregnancy test within 7 days prior to DXA scan is available, the pregnancy test does not need to be repeated.

f If result is below the lower limit of normal refer to section 7.2 and 7.3.

g Subjects who have vitamin D levels ( $D_2+D_3$ ) <20 ng/ml at Day 90 will not be eligible for randomization per section 6.2.

h L1-L4 and total body scans with body composition.

i Subjects at the University of Minnesota (UMN) only.

j All subjects will begin taking supplemental vitamin D per day and calcium, if needed, to meet recommended dietary allowance (RDA) requirement upon admission to the hospital for the HCT and continue through Day 360. If a subject has low vitamin D ( $D_2+D_3$ ), dietary calcium intake is below RDA, or the ionized/or corrected calcium level is below the normal range, additional vitamin D and/or calcium supplementation will be given per Section 7.3.

k For subjects randomized to the Pamidronate Group, 1 mg/kg (60 mg max) will be administered via intravenous (IV) infusion over 4 hours. Subjects will be given 15 mg/kg acetaminophen (or maximum of 500 mg) prior to infusion then every 4 hours as needed for a maximum of 24 hours. Postmenarchal subjects randomized to pamidronate will be put on an oral contraceptive pill (Loestrin or Orthocept or other OCP that contains 30 mcg ethinyl estradiol), birth control patch or other effective method of birth control. The results of the serum creatinine and pregnancy test (if applicable) must be reviewed before drug administration.

l Pamidronate patients only

m Serum creatinine level and spot urine collected the morning after each pamidronate infusion; however if not feasible at that time may be done anytime within 7 days after pamidronate infusion. A morning collection is preferred, but not mandatory. The time of the urine collection must be recorded.

### **8.1.1 Study Protocol Compliance/Treatment Adherence**

All doses of pamidronate will be administered at the clinical site.

For all subjects, adherence to the calcium and vitamin D regimen described in Section 7 will be evaluated by querying subjects every 3 months either at study visits or by telephone.

### **8.1.2 Deviations from the Clinical Protocol**

When a deviation from the protocol is necessary for an individual subject, the Investigator must contact the Sponsor prior to the deviation (unless the deviation is safety related). The subject may continue in the study by mutual agreement of the Sponsor and the Investigator. A description of the deviation from the protocol and justification must be recorded on the Protocol Deviation Form.

### **8.1.3 Subject Compensation Guidelines**

A\$50 gift card will be given to each participant at study enrollment and at the Day 90 and 360 visits to partially compensate for the extra time required for study related tests and procedures on days of routine transplant associated visits.

Travel reimbursement (gas, parking, meals) will be offered at Day 270 study visit as it does not coincide with an institution's standard post-HCT follow-up.

Reimbursement (lodging, meals) will be offered to patients assigned to pamidronate at Day 180 and 270 visits for an overnight stay and meals in order to obtain the study related 24 hour post-infusion lab work.

It is recognized that this is a multi-center trial and the reimbursement days may differ between institutions. Therefore the above is a considered a guideline. Each institution's treatment consent will document the specific visits for their site which will be eligible for reimbursement.

Reimbursements will be made following individual institutional usual practice.

## **8.2 Clinical Procedures**

### **8.2.1 Medical History**

A study physician and/or study coordinator will review the following with the subject/parent(s) or legal guardian(s):

- Current and past prescription medications and doses (including calcium, vitamin D, oral contraceptives, estrogen or testosterone replacement, gonadotropin-releasing hormone [GnRH] analogs, L-thyroxine, glucocorticoids, and growth hormone),
- current and past medical history (with particular attention to fracture history, age at menarche, date of the last menstrual period, history of delayed puberty, and chronic inflammatory diseases), and
- family history

The subject's medical history will be reviewed at each study visit. This will include medical chart review and query of the subject and parent(s) or legal guardian(s) (as applicable) regarding any changes since the last study visit.

Pre-transplant treatment exposure data will be abstracted from the subject's medical records, including pre-transplant chemotherapy (agent and total cumulative doses, including glucocorticoids) and radiation therapy (sites and total cumulative doses with particular attention to cranial radiation). Transplant treatment exposure data is maintained in the electronic database of the Blood and Marrow Transplant programs at both sites and includes specific chemotherapy agents utilized in the transplant preparative regimen, dose of TBI (if given), and prophylaxis and/or treatment (glucocorticoids) for graft- versus-host disease (GVHD).

If a subject assigned the control arm is unwilling to return to the clinical site

for any visits not associated with a routine post-HCT follow-up, the subject or their parent(s)/legal guardian(s) will be contacted via telephone to discuss any changes in health since their last study visit.

